4. CHANGES IN THE CONDUCT OF THE STUDY OR PLANNED ANALYSIS

Not applicable.

5. ANALYSIS SETS

The following three analysis sets defined:

- The Safety set consists of all subjects who received treatment;

- The Full Analysis Set (FAS) consists of all randomized subjects (equivalent to the Intent-to-Treat [ITT] set).
- The Per-Protocol (PP) set consists of all FAS subjects who have no major protocol deviations.

Major protocol deviations are deviations that have an impact on the primary endpoint, or that have an impact on the randomization assignment. These will be determined prior to database lock.

6. DEMOGRAPHIC AND OTHER BASELINE CHARACTERISTICS

6.1 Demographic and other baseline characteristics

Demographic and other baseline data will be summarized descriptively for subjects in each treatment group in the FAS set. The categorical data will be summarized descriptively by frequencies along with the associated percentages. The continuous data will be presented using summary statistics such as number of subjects, mean, standard deviation, minimum, median and maximum.

The following demographic variables will be summarized:

- Age;
- Gender;
- Race/ethnicity;
- Height;
- Weight;
- Body mass index;
- Indication of subject being of child bearing age;
- History of SVT, DVT/PE;
- Family history of DVT/PE;
- History of alcohol abuse;
- Smoking status.

In addition, the following screening and baseline data will be collected:

- Physical examination, including documentation of relevant medical and surgical history;
- Complete blood count (CBC) with white blood cell differential, liver function tests and electrolytes;
- Documentation of medical history including all concomitant medications during 24 hours prior to surgery;
- Review of inclusion / exclusion criteria to confirm subject eligibility.

7. PROCEDURE DATA

Procedure data will be summarized descriptively for subjects in each treatment group in the FAS set to assess comparability of treatment groups. The categorical data will be summarized descriptively by frequencies along with the associated percentages. The continuous data will be presented using summary statistics such as number of subjects, mean, standard deviation, minimum, median and maximum.

The following procedure variables will be analyzed:

- Operative procedure, including type of approach, indication for surgery and tumor location, if applicable;
- Operating room (OR) time;
- Procedure duration (from first incision to closure completion);
- Specification of treatment to which subject is randomized;
- CSF leak determination;
- For patients treated with EVICEL, the following data will be analyzed for first EVICEL application and second treatment of EVICEL (if applicable): method of EVICEL application, number of layers applied, indication of spontaneous leak observation, indication of Valsalva maneuver performed after randomized treatment application (if applicable), indication of CSF leak detection after Valsalva, definition of leak (if applicable), and type of tip used.
- EVICEL application summary data, such as total number of kits used, approximate total amount of EVICEL used, derived volume per kit, and indication of watertight closure observed;
- For patients treated with Additional Sutures, number of sutures applied, indication of spontaneous leak observation, indication of Valsalva maneuver performed after randomized treatment application (if applicable), indication of watertight closure observed, and indication of additional treatment required for durability of the dura closure (suture, collagen, oxidized regenerated cellulose and/or other treatment);
- Indication and specification of standard of care method for rescue therapy applied, such as DuraSeal, BioGlue, other glues, hemostatic matrices, autologous and biologic dural patches;
- Length of subject hospital stay (from hospital admission to hospital discharge, as well as from procedure to hospital discharge).

8. EFFECTIVENESS

8.1 General methods of analysis

The Clinical Data Management and Biostatistics groups within Clinical Development at ETHICON will be responsible for the overall analysis of data from this protocol. All analyses/summaries will be produced using SAS® (Version 9.1 (EG) or later).

Data will be summarized descriptively for subjects in each treatment group in the FAS set. The categorical data will be summarized descriptively by frequencies along with the associated percentages. The continuous data will be presented using summary statistics such as number of subjects, mean, standard deviation, minimum, median and maximum.

8.2 Primary effectiveness analysis

The primary effectiveness endpoint is the proportion of success (intraoperative watertight closure) in the treatment of intraoperative CSF leakage defined as no CSF leakage from dural repair intraoperatively, during a Valsalva maneuver 20-25 cm H₂O for 5-10 seconds.

No formal sample size calculation has been performed for this study. The sample size required for the trial is 42 randomized paediatrics subjects recruited from 6-8 sites within the European Union. This sample size is considered adequate by EMA Paediatric Investigation Plan to summarize the data descriptively.

The primary effectiveness endpoint will be analyzed using the FAS and the PP set. However, the primary analysis will be based on the FAS. The PP analysis will be considered confirmatory.

In all cases, treatment allocation will be based on randomization for the primary effectiveness endpoint using the FAS. If more than two subjects are mis-randomized, then an additional confirmatory analysis based on treatment received will be performed for the primary effectiveness endpoint, using the FAS.

The proportion of successes will be summarized descriptively by treatment group. In addition, a two-sided 95% confidence intervals (CIs) will be reported for the ratio of the proportion of success in the EVICEL group/proportion of success in Control group (P_E/P_C), using the Farrington-Manning score method.

8.3 Secondary effectiveness analysis

No secondary effectiveness data will be collected for this study.

8.4 Analysis of follow-up data

The following follow-up data will be summarized descriptively for 5-day (± 2 days) and 30-day (± 3 days) visits:

- Re-hospitalizations and surgical procedures since previous study visit;
- Relevant changes in medical history and concomitant medications since screening;
- Presence of clinically significant changes to subject since baseline;
- Surgical site assessment, including presence of infection (brain abscess, meningitis, and/or surgical site infection), hematoma (intradural, extradural, and/or subcutaneous), pseudomeningocele, and other surgical site experience;
- Wound healing assessment data;
- CSF leak determination data;
- Laboratory data (complete blood count with differential, creatinine, liver function tests and electrolytes) (for 5-day only).

8.5 Statistical/analytical issues

8.5.1 Handling of dropouts or missing data

For the primary effectiveness endpoint, the analysis for the FAS set will be performed considering missing data as failures; in addition, sensitivity analyses for the FAS set will be performed considering missing data as successes, and, as worst-case, with missing data for the EVICEL group considered as failures and missing data for the Control group considered as successes.

If there are incomplete dates and calculations (e.g. time since procedure) are needed, the following rules are used (no rules will be applied for missing years; this data would normally be expected to be queried):

- Missing date which includes the procedure data: the rules below are followed unless the derived date is pre-procedure, when the derived date will be 1st day after the procedure.
- Missing day: 15th used

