9.7 Collection of Adverse Events

AEs will be recorded as they are reported, whether spontaneously volunteered or in response to questioning about well-being. AEs will be collected from the point of randomization during the surgical procedure, throughout the hospital admission, and until completion of the 30-day follow-up visit.

All AEs will be documented in the subject's source documents (e.g. medical records) and eCRF. All AEs will be followed until completion of the 30-day follow-up visit or until a stable resolution, whichever is sooner.

Details of all AEs occurring during the study must be recorded on the AE form with the following information:

- Description of the event
- Dates of onset and resolution
- Severity
- Action taken
- Outcome
- Relationship to investigational product
- Whether the AE is serious or not

Expectedness of an SAE will be defined based on whether the specificity or severity of which is not consistent with the current investigator brochure.

Other: The investigator may also need to consider whether an event is attributable to the investigational product, based on insufficiencies or inadequacies in the instructions for use or as a result of user error. The investigator must contact the Sponsor should this occur.

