10.3 Listings

Listings will be presented in centre, subject and visit order. The listings will be produced using the data from all subjects.

The columns indicate the listings that will be included in the report. All data available on the database, with the exception of fields used for administration, e.g. signature fields, will be included in the listing for the report.

Missing data will be shown by a space.

10.3.1 Appendix 16.2 listings:

All listings will be prefixed with 16.2.

No	Title of listing	Notes	CRF Page
1	Disposition of subjects		
1.1	Disposition of subjects	Includes reason for withdrawal and time to withdrawal	54
1.2	Visit dates	Includes informed consent and discharge details Includes derived data: -Nights in hospital -Days from procedure	Various
2	Protocol deviations		
2	Protocol deviations		50 and 52
3	Subjects excluded from the analysis		
3	Definition of analysis sets	As defined in Section 5 of this SAP	

No	Title of listing	Notes	CRF Page
4	Baseline characteristics		
4.1	Demographics, special histories, smoking status, and subject eligibility		8 and 10
4.2	Physical exam / medical / surgical history		12, 14, and 16
4.3	Inclusion and exclusion criteria		5
4.4	Concomitant medications	Derived data: -Days from procedure to start -Duration of Con Med	46 and 48
5	Surgical details		
5.1	Surgical procedure - re-operative information, timings including operation room and length of procedure, initial CSF leak determination, and randomization data	Includes derived data: -Time in the operating room -Length of procedure	18, 20, and 22
5.2	Surgical procedure – EVICEL application details		24 and 25
5.3	Surgical procedure – EVICEL application summary		25
5.4	Surgical procedure - Additional Sutures treatment details		28
5.5	Surgical procedure – Standard of Care methods for rescue therapy		30 and 31
6	Effectiveness data		
6.1	Effectiveness - primary effectiveness endpoint		
6.1	Primary effectiveness endpoint - Success (no CSF leak preoperatively during Valsalva maneuver) - FAS (sensitivity analysis) and PP set	Includes derived data: For ITT, missing data considered as: -Analysis#1 (primary): failures (d) Sensitivity analysis - missing data considered as: -Analysis#2: successes (d); -Analysis#3: failures for EVICEL and successes for Control (d)	
6.2	Follow-up assessments		
6.2.1	Post-surgery to hospital discharge assessment – length of hospital stay	Includes derived data: -Days from admission to discharge -Days from procedure to discharge	1

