6.2.2	5-day (± 2 days) and 30-day (± 3 days) follow-up assessments		1 and 34
7	Safety data		
7.1	Adverse event listings (each subject)		
7.1.1	Adverse events	Includes derived data: -Days from procedure to start -Duration of AE	40, 42 and 43
7.1.2	Adverse event comments		42

No	Title of listing	Notes	CRF Page
7.1.3	Adverse events (MedDRA codes)		40, 42 and 43
7.1.4	Serious adverse events		40, 42 and 43
7.2	Laboratory data		
7.2.1	Laboratory data - Complete Blood Count	At baseline and at 5-day follow-up	37
7.2.2	Laboratory data - White Blood Cell Differential	At baseline and at 5-day follow-up	37
7.2.3	Laboratory data – Creatinine, Liver Function Tests and Electrolytes	At baseline and at 5-day follow-up	37
7.3	Other safety data		
7.3	Safety/secondary endpoints	Includes derived data: -Incidence of CSF leakage within 5 days (± 2 days) post-operatively -Incidence of CSF leakage within 30 days (± 3 days) post-operatively -Incidence of surgical site infections (SSI) according to National Healthcare Safety Network (NHSN) criteria within 30 days (± 3 days) post-operatively (separately for any SSI, superficial incisional SSI, deep incisional SSI, and organ/space SSI)	24, 25, 28, and 34

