10.3.2 Data review

Listings will be available for regular listing reviews to be organized by Data Management.

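### Does the missing-day rule in SAP 8.5.1 need an upper limit for adverse event and medication dates?

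*SAP*

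**What the plan says.** SAP 8.5.1 has two rules for incomplete dates, used only when a quantity such as time since the procedure must be calculated. The default is "Missing day: 15th used". It applies "unless the derived date is pre-procedure, when the derived date will be 1st day after the procedure". Missing years have no rule and are expected to be queried. No upper limit appears in this section or elsewhere in the SAP.

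Protocol 9.7 sets the window for adverse events: "AEs will be collected from the point of randomization during the surgical procedure", "throughout the hospital admission, and until completion of the 30-day follow-up visit". Day 0 is therefore a valid onset day. The last valid day is that of the final visit, day 27 to 33 under the 30 ± 3 day window. The same section requires both onset and resolution dates.

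The derived dates feed two listings in SAP 10.3.1. Listing 7.1.1 gives days from procedure to start and "Duration of AE". Listing 4.4 gives the matching interval for medications and "Duration of Con Med". The listings also print "All data available on the database", apart from administrative fields, and SAP 10.3.2 adds: "Listings will be available for regular listing reviews".

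**The concern.** The rule guards one side only. A derived date cannot fall before surgery, but it can fall after the final visit or after the end date recorded for the same event. A negative duration, or an onset after follow-up has closed, is impossible, and in a trial of 42 children the individual safety listings are likely to be read line by line. The rule also rarely leaves an intraoperative event on day 0, although collection starts in the operating room.

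If these dates decided which events were counted, or whether a leak fell inside the 5-day or 30-day window, the safety results could shift.

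**Working it through.** The plan states no figure here, so the rule was applied literally to a grid of dates.

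**Inputs.**
- The rule, from SAP 8.5.1.
- True onset on day 0 to day L (Protocol 9.7), where L is the day of the last visit: 27, 30 or 33.
- Assumptions: all 365 surgery dates of a non-leap year, and every onset day, carry equal weight.

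**Formula.** With P the surgery date, D = the 15th of the recorded month; if D < P, then D = P + 1.

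**1. Start dated after the last visit (D > P + L).** The grid has 365 × (L + 1) combinations.

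| L | Count | Share |
|---|---|---|
| 27 | 1260/10220 | 12.3% |
| 30 | 1260/11315 | 11.1% |
| 33 | 1260/12410 | 10.2% |

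The 15th lies at most 14 days after the true onset. This can therefore happen only if the true onset is on or after day 14, 17 or 20 respectively (L − 13). The share depends on how many events start that late. If onsets instead decline exponentially after surgery, with assumed means of 3, 5 or 10 days, the share is about 0.01–0.1%, 0.3–0.9% or 2–4% across the three values of L.

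**2. Start dated after the recorded end.** Taking every end day from onset to L:

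| L | Count | Share |
|---|---|---|
| 27 | 30005/148190 | 20.2% |
| 30 | 33785/181040 | 18.7% |
| 33 | 37565/217175 | 17.3% |

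This also depends on the assumed pattern. With L = 30, the share is 47.7% for events that end on the day they start and 23.0% for events that end 7 days later.

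**3. Day-0 events.** Surgery falls before the 15th on 168 dates, and there the default moves the event to the 15th. It falls after the 15th on 185 dates, and there the replacement moves it to day 1. The event stays on day 0 only on the remaining 365 − 168 − 185 = 12 dates. The two rules thus contribute about equally.

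**4. What a cap would gain.** Suppose the start were limited to the earlier of the recorded end and the last visit. Both kinds of impossible value disappear. For L = 33 the mean absolute error in the start day goes from 6.82 to 6.27 days with no end date, and from 6.24 to 5.28 days with a known end date. The gain is about half a day and just under one day; the imputed day remains a rough guess. Also moving the lower limit to the surgery date would be less accurate than the cap alone (5.43 against 5.28 days with a known end date).

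**5. What uses the derived dates.**
- The primary endpoint is read during surgery and uses no imputed date.
- Adverse event tables 3.1.1 to 3.1.6 (SAP 10.2.2) pool events during and after treatment. Every derived date is on or after surgery, so no event drops out.
- Leak and infection incidence (listing 7.3) is drawn from CRF pages 24, 25, 28 and 34. The adverse event listing is drawn from pages 40, 42 and 43. The incidences therefore do not rest on imputed event dates.
- SAP 9.4 makes all safety analysis descriptive.

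Only the two derived fields in each of listings 7.1.1 and 4.4 remain.

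**The case for a change.** The strongest case for a change is that an impossible value in a safety listing is an error however rare it is. The remedy would be one paragraph and a few lines of code, using dates the SAP already lists, and a date rule is better fixed before anyone sees the records. Listing reviews and queries do not set a derivation rule, and SAP 8.5.1 expects queries for missing years but imputes missing days.

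Much of this stands. The rule has no upper limit, and the counts are right. The wording that introduces the replacement is also garbled. It can be read as covering only the month of surgery or all incomplete dates. Adverse events come out the same either way, but a medication recorded as starting in an earlier month would not.

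What does not stand is the step from there to a needed change. The imputation is easy to recognise, because the collected partial date is printed in the same listing. A negative duration is an obvious target for the edit checks of Protocol 12.3, and Protocol 13.1 has monitors check completeness about every four to six weeks. A programmer who meets such a record can limit the date to the recorded end without affecting any result. The day-0 point is a trade-off: with the surgery date as lower limit, day 0 is kept on 197 dates instead of 12, but correct day-1 onsets fall from 185 to 12.

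**Conclusion.** The observation is correct but changes nothing that the trial will report as a result. It concerns derived start days and durations in two listings, for an unknown and possibly zero number of records. Given a missing day, roughly one start in ten would pass the last visit and about one in five or six would pass its own end date. Both figures assume evenly spread onsets, and the first falls below 1% if onsets average 5 days or less after surgery. No table, endpoint, incidence or conclusion depends on these fields. The gap is one that a programmer closes sensibly if a case arises, so the plan can stand as written.

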8.5.2 Interim analyses and data monitoring

No interim analysis will be performed for this study.

8.5.3 Multiple comparison / multiplicity

Not applicable.

9. SAFETY EVALUATION

9.1 Adverse events

The safety/secondary endpoints listed in section 3 will be summarized using the Safety set.

9.2 Clinical laboratory evaluation

Blood samples will be taken for Complete Blood Count (CBC) with differential, creatinine, liver tests and electrolytes at baseline and at 5 day (\pm 2 days) visit.

9.3 Vital signs, physical findings and other observations related to safety

Vital signs will not be collected in this study. A physical exam will be performed and medical/surgical history data will be collected at screening. In addition, a physical exam will be performed at 5 day (\pm 2 days) and 30-day (\pm 2 days) visits.

10. DATA PRESENTATION

The report forms part of an integrated clinical study report. The actual numbering of tables, listings and other outputs may change. Numbering is in accordance with ICH guideline E3².

10.1 Procedure or treatment labels

The following labels will be used for all output: **EVICEL** and **Control**.

10.2 Tables and figures

Data will be tabulated by treatment group and, if appropriate, by visit. Continuous data summaries will present (unless stated otherwise) number of observations, number of missing observations (if there are any), mean, standard deviation, minimum, median and maximum. Categorical data summaries will present the number of observations and the corresponding percentage. The following tables will be produced:

10.2.1 In-text tables and figures

These will be produced for the main report in conjunction with the medical writer. These will include, but will not be limited to:

No	Title of table/figure	Notes
F1	Subject disposition	Based on Table 14.1.1.4

No	Title of table/figure	Notes
T1	Demographic characteristics – FAS analysis set	Summary of Table 14.1.2.1
T2	Surgical procedure – FAS analysis set	Summary of key items from Tables 14.1.3.1-14.1.3.7
T3	Statistical summary for primary effectiveness endpoint – Per-Protocol and FAS analysis sets (including sensitivity analysis summary)	Summary of Tables 14.2.1.1 and 14.2.1.2
T4	Summary of AEs occurring in >5% of subjects – Safety analysis set	Summary of 14.3.1.3

T=Table F=Figure

10.2.2 Section 14 tables

Shell tables shown in Appendix 1, according to the code in the 'Shell' column. All table numbers will be prefixed with 14.

No	Title of table/figure	Notes	Shell ¹
1.1	Disposition of subjects, analysis sets and protocol deviations		
1.1.1	Disposition of subjects by centre – FAS	Includes number withdrawn – by center	DS
1.1.2	Enrollment by center – FAS	By center	E
1.1.3	Summary of protocol deviations – FAS	Includes both minor and major protocol deviations	PD
1.1.4	Analysis sets – FAS		ST
1.2	Baseline data	Excludes baseline data that is also measured post procedure and/or safety data	
1.2.1	Demographics – FAS	Age, height, weight, BMI – continuous data (c); gender, race, ethnicity, indication of subject being of child bearing age, history of SVT, DVT/PE, family history of DVT/PE, history of alcohol abuse, smoking status – all discrete data (d)	DG
1.2.2	Baseline characteristics – FAS	Presence of relevant history of prior surgery, indication of any relevant changes in medical history between screening and 24 hours before procedure, and confirmation of subject eligibility - all (d)	G1 ²
1.2.3	Physical exam / medical / surgical history – FAS	Includes frequencies	HX
1.3	Operative data		
1.3.1	Pre-operative data – FAS	Operative procedure, type of approach, indication for surgery, and tumor location (if applicable) - all (d)	G2

¹ Shell: Example table from Appendix 1 (Shell tables). Letters refer to standard output, numbers to project specific output.

² For Tables G1, G2, G3 notes will indicate if data is continuous or discrete.

No	Title of table/figure	Notes	Shell ¹
1.3.2	Operative data: CSF leak determination and randomization data – FAS	Indication of spontaneous CSF leak observation, indication of Valsalva maneuver performed, indication of CSF leak observed, and specification of treatment to which subject is randomized – all (d)	G2
1.3.3	Operative data: EVICEL application – FAS	For patients treated with EVICEL, the following data will be analyzed for first EVICEL application and second treatment of EVICEL (if applicable): method of EVICEL application, number of layers applied, indication of spontaneous leak observation, indication of Valsalva maneuver performed after randomized treatment application (if applicable), definition of CSF leak observed (if applicable), indication of CSF leak detection after Valsalva (if applicable), definition of leak (if applicable), and type of tip used - all (d)	G2
1.3.4	Operative data: EVICEL application summary – FAS	Total number of EVICEL kits used (both d and c), approximate total amount of EVICEL used (mL) (c), derived volume per kit (mL) (c), and indication of watertight closure observed (d)	G2
1.3.5	Operative data: Additional Sutures treatment details – FAS	For Control patients, number of sutures applied (c), indication of spontaneous leak observation, indication of Valsalva maneuver performed after randomized treatment application (if applicable), indication of watertight closure observed, and indication of additional treatment required for durability of the dura closure (any additional treatment, suture, collagen, oxidized regenerated cellulose and/or other treatment) – all (d)	G2
1.3.6	Operative data: Standard of Care methods for rescue therapy – FAS	Indication of DuraSeal use (d), number of DuraSeal 5 mL kits used (both c and d), indication of BioGlue use (d), size of BioGlue kits used (d), indication of other glues use (d), indication of hemostatic matrix use (d), predefined hemostatic matrix size used (d), indication of autologous dural patch used (any location, fascia, pericranium, fat, muscle, other autologous dural patch) (d), and biologic dural patch use (d)	G2
1.3.7	Operative data timings – FAS	Time in operating room (c), length of procedure (from first incision to closure completion) (c)	G2
2	Effectiveness data		
2.1	Primary endpoint: success (no CSF leak intraoperatively during Valsalva maneuver)	Includes sensitivity analyses; Includes two-sided 95% CI for the ratio proportion of successes in EVICEL group/proportion of successes in Control group	
2.1.1	Success (no CSF leak intraoperatively during Valsalva maneuver): primary effectiveness analysis – FAS	Missing data considered as: -Analysis#1 (primary effectiveness analysis): failures (d) Sensitivity analysis - missing data considered as: -Analysis#2: successes (d); -Analysis#3: failures for EVICEL and successes for Control (d)	G2
2.1.2	Success (no CSF leak intraoperatively during Valsalva maneuver): sensitivity analysis – PP set	Discrete data	G2

No	Title of table/figure	Notes	Shell ¹
2.2	Follow-up assessments		
2.2.1	Post-surgery to hospital discharge assessment: length of hospital stay - FAS	Length of subject hospital stay from admission to discharge (days), length of subject hospital stay from procedure to hospital discharge (days) (c)	G2
2.2.2	5-day (± 2 days) and 30-day (± 3 days) follow-up assessments – FAS	Indication of re-hospitalizations since previous study visit, indication of surgical procedures since previous study visit, indication of relevant changes in medical history since screening, presence of clinically significant changes to subject since baseline, surgical site assessment, including presence of infection (brain abscess, meningitis, and/or surgical site infection – superficial incisional, deep incisional and/or organ-space), hematoma (intradural, extradural, and/or subcutaneous), pseudomeningocele, and other surgical site experience, wound healing assessment, CSF leak determination - all (d)	G2
3	Safety data		
3.1	Adverse Events		
3.1.1	Number of subjects experiencing any during/post treatment AE by category – Safety analysis set		AS
3.1.2	Adverse events (during/post treatment) by subject, MedDRA preferred term and system organ class – Safety analysis set		AM
3.1.3	Summary of during/post treatment adverse events by subject and coded terms, preferred terms occurring in $\geq 5\%$ of subjects – Safety analysis set		AM
3.1.4	Summary of during/post treatment serious adverse events by subject and coded terms – Safety analysis set	Includes adverse events for which the answer for CRF question “Serious?” in the CRF is “Yes”	AM
3.1.5	Summary of during/post treatment surgical procedure related (possibly, definitely) adverse events by subject and coded terms – Safety analysis set	Includes adverse events for which the answer for CRF item “Relationship to surgical procedure” is “Possibly related” or “Related”.	AM
3.1.6	Summary of during/post treatment study treatment related (possibly, definitely) adverse events by patient and coded terms – Safety analysis set	Includes adverse events for which the answer for CRF item “Relationship to study treatment” is “Possibly related” or “Related”.	AM

No	Title of table/figure	Notes	Shell ¹
3.2	Laboratory data	Reported in SI units	
3.2.1	Laboratory data: Complete Blood Count - Safety analysis set	At baseline and at 5-day follow-up	L
3.2.2	Laboratory data: White Blood Cell Differential - Safety analysis set	At baseline and at 5-day follow-up	L
3.2.3	Laboratory data: Creatinine, Liver Function Test and Electrolytes - Safety analysis set	At baseline and at 5-day follow-up	L
3.3	Other safety data		
3.3	Safety/secondary endpoints – Safety analysis set	Incidence of CSF leakage within 5 days (\pm 2 days) post-operatively, incidence of CSF leakage within 30 days (\pm 3 days) post operatively, and incidence of surgical site infections (SSI) according to National Healthcare Safety Network (NHSN) criteria within 30 days (\pm 3 days) post-operatively (separately for any SSI, superficial incisional SSI, deep incisional SSI, and organ/space SSI) – all (d)	G2

Note: ‘-’ indicates a new line in the title.

